Study Protocol

Title

Temporary Aortic Occlusion with the Abdominal Tourniquet for Refractory Postpartum Haemorrhage: A Proof-of-Concept Study in a War-Affected Region

Version

1.0

Date

November 1, 2024

Principal Investigators

[name], MD, PhD — Olexandrivska Hospital, Zaporizhzhia

[name], MD, PhD, DMSc — Uniklinika Medical Centre, Kyiv

Institution

Olexandrivska Hospital, Zaporizhzhia, Ukraine

Ethics Approval

Approved by Olexandrivska Hospital Ethics Committee (Approval number: 2024/EC/128094)

1. Background and Rationale

Postpartum haemorrhage (PPH) remains the leading cause of maternal mortality globally, especially in low-resource and crisis-affected settings. In Ukraine, full-scale war has disrupted medical infrastructure, limiting access to timely surgical interventions and blood transfusion.

The AAJT-S (Abdominal Aortic and Junctional Tourniquet – Stabilized) is an FDA-approved device for temporary aortic occlusion in trauma, but its use in obstetrics is not well studied. This study aims to evaluate the feasibility, safety, and preliminary clinical efficacy of AAJT-S in controlling refractory PPH due to uterine atony in a wartime environment.

2. Objectives

Primary Objective:

- To assess whether the AAJT-S device can temporarily and safely control severe PPH in a resource-limited, high-risk setting.

Secondary Objectives:

- To describe feasibility of AAJT-S deployment by obstetric teams.
- To evaluate maternal hemodynamic stabilization and procedural outcomes.

- To monitor for short- and long-term complications (thrombosis, ischemia, infection, renal dysfunction).

3. Study Design

- Design: Prospective, open-label, non-randomized, proof-of-concept
- Duration: December 2024 – April 2025
- Setting: Olexandrivska Hospital, Zaporizhzhia, Ukraine
- Sample Size: 4 patients

4. Inclusion/Exclusion Criteria

Inclusion Criteria:

- Age \geq 18 years
- Primary PPH with blood loss >1000 mL
- Refractory to uterotronics and uterine balloon tamponade
- Oral informed consent obtained

Exclusion Criteria:

- PPH due to trauma, coagulopathy, or retained placenta
- Inability to provide informed consent

5. Intervention

Application of the AAJT-S device over the upper abdomen (inflated to 250 mmHg) to achieve temporary aortic occlusion for \leq 60 minutes. Device application was done following persistent bleeding despite standard therapy.

6. Procedures

- Initial PPH management per hospital protocol: oxytocin, misoprostol, methylergometrine, tranexamic acid, uterine massage, balloon tamponade
- AAJT-S deployed in case of ongoing bleeding >1000 mL
- Device monitored and deflated after stabilization or readiness for surgery
- Surgical treatment (compression sutures, artery ligation) performed if bleeding resumed
- Data captured: demographics, interventions, outcomes, adverse events
- Follow-up: inpatient daily assessments, phone monitoring post-discharge, pelvic ultrasound at 6 and 12 months postpartum

7. Outcomes

Primary Outcome:

- Control of bleeding within 2 minutes after AAJT-S application

Secondary Outcomes:

- Surgical readiness time gained
- Total blood loss and transfusion requirements
- Postoperative complications
- Long-term recovery indicators

8. Statistical Considerations

Descriptive statistics only (medians, ranges); no hypothesis testing or power calculation due to pilot nature. Outcomes presented per individual case.

9. Ethical Considerations

- Approved by the institutional ethics committee (2024/EC/128094)
- AAJT-S used off-label with oral informed consent
- Risks and rationale explained to each participant

10. Dissemination Plan

- Results to be submitted for peer-reviewed publication
- Presented at conferences on maternal health and obstetric innovation

1.1. Primary Objective

- To assess the feasibility and preliminary effectiveness of the AAJT-S device in controlling refractory postpartum haemorrhage (PPH) due to uterine atony in a war-affected, resource-limited setting.

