1.2. Secondary Objectives

- To evaluate the safety profile of the AAJT-S device (device-related complications, thrombotic events, ischemic injuries, infection).
- To assess the duration of bleeding control and time to definitive surgical intervention.

2. Study Design

- **Design:** Prospective, single-center, open-label, non-randomized, proof-of-concept study.
- **Sample Size:** 4 patients
- **Analysis Type:** Descriptive statistics only. No inferential testing or hypothesis-driven comparisons will be performed due to small sample size and exploratory nature.

3. Analysis Populations

- **Full Analysis Set (FAS):** All patients who received AAJT-S for refractory PPH.
- **Safety Population:** Identical to FAS; all patients who underwent device placement and were monitored until discharge.

4. Variables

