4.2. Effectiveness Outcomes

- **Time to bleeding control** (minutes from inflation to cessation of visible bleeding)
- **Total duration of AAJT-S placement** (minutes)
- **Definitive surgical interventions performed** (Yes/No; type of procedure)
- **Total cumulative measured blood loss (CMBL)** (mL)
- **Need for blood transfusion** (Yes/No; units PRBC and FFP)

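### Feasibility is half of the SAP's primary objective, but no variable is designated to measure it, and the analysis set begins only once the device has been received

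*SAP*

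**What the plan says.** SAP 1.1 gives a two-part primary objective: "To assess the feasibility and preliminary effectiveness of the AAJT-S device". Protocol section 2 places feasibility among the secondary objectives and gives it a narrower meaning: "To describe feasibility of AAJT-S deployment by obstetric teams".

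The design in Protocol section 3 is "Prospective, open-label, non-randomized, proof-of-concept", with four patients between December 2024 and April 2025. Neither document says how the four are to be chosen from the women who qualify.

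SAP section 3 defines the Full Analysis Set (FAS) as "All patients who received AAJT-S for refractory PPH". The safety population is "Identical to FAS; all patients who underwent device placement and were monitored until discharge".

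SAP section 4 has three groups of variables: baseline, effectiveness and safety. Time to bleeding control is counted in "minutes from inflation to cessation of visible bleeding". Duration of placement is also listed under effectiveness. Incorrect placement is mentioned in SAP 4.3, as an example of a device-related complication. The outcome list in Protocol section 7 has no deployment measure.

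**The concern.** Whether obstetric teams can deploy the device is settled before and during application: was it available and tried, was it brought to full inflation in the right position, and how long did that take from the decision? The plan's time to bleeding control starts after those steps, and its analysis set is made up of women for whom they have already ended in receipt.

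If the plan is followed exactly, part of the SAP's primary objective has no pre-specified result. Any feasibility statement in the report would have to be constructed after the data were seen, from items listed for other purposes.

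There is also a selection problem. In an uncontrolled series of four, much of what a reader can conclude depends on how those four came to be treated. Without a consecutive rule or a record of eligible women who were not treated, that cannot be assessed.

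**Working it through.** **The plan's own figure.** The sample size of 4 (Protocol section 3, SAP section 2) comes with no error rate, power or target rate, and Protocol section 8 says that no power calculation was made. There is nothing to reproduce. The check concerns denominators and which variables exist.

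**Step 1. What a feasibility assessment needs, against what is listed.**

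| Question | Variable in SAP section 4 or Protocol section 7 |
|---|---|
| How many women were eligible? | None |
| In how many was placement attempted? | None |
| Was the device correctly placed? | Only as an example of a complication (SAP 4.3), among recipients |
| How long from decision to full inflation? | None; the SAP's time to bleeding control starts at inflation |
| How many repositionings? | None |
| What would count as feasible? | No criterion |

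The protocol's primary outcome (bleeding control within 2 minutes) and its outcome on time gained for surgery both follow application, so they do not fill these gaps.

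**Step 2. Device receipt within the FAS.** Rate = recipients / FAS members. Receipt defines membership, so the rate is 4/4 = 100% for any data.

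**Step 3. Correct placement within the FAS.** With k incorrect placements recorded among the four, rate = (4 − k)/4:

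- k = 0: 4/4 = 100%
- k = 1: 3/4 = 75%
- k = 2: 2/4 = 50%

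The FAS does not force this figure to 100%.

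**Step 4. Uptake among eligible women.** Suppose placement was attempted in four women and m further eligible women had no attempt. The documents give no value for m, so this range is an assumption. Uptake = 4/(4 + m):

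- m = 0: 4/4 = 100%
- m = 1: 4/5 = 80%
- m = 2: 4/6 = 66.7%
- m = 4: 4/8 = 50%

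The planned tables would be the same in all four cases, because women without the device appear nowhere.

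**Step 5. Who is lost.** Two groups must be kept apart. A woman who received the device but had it wrongly placed, or whose bleeding was not controlled, is in the FAS, and SAP 4.2 and 4.3 can capture her. An eligible woman who was never treated, or in whom the attempt was abandoned before the device counted as received, is not. The SAP does not say at what point a failed attempt becomes receipt.

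**The case against.** The strongest reply is that this is a four-patient, descriptive proof of concept. It makes no inference, presents outcomes case by case (Protocol section 8), and admits its small size and lack of a control group (SAP section 7). Protocol section 6 gives a trigger for deployment, so use of the device is not left wholly open. Incorrect placement can be recorded, and time to control and duration of placement bear on feasibility indirectly.

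Much of this is fair and limits the point. But case-by-case reporting of recipients cannot show who was not treated. A trigger says when the device should be used, not how often it was. The stated limitations do not mention selection.

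Three stronger readings are tempting, and the documents do not support them:

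- A reader might infer that deployment success is 100% by construction. That holds for receipt only. The SAP defines no deployment success, and Step 3 shows that the figure for correct placement can fall.
- A reader might infer that the primary objective as a whole cannot be answered. Its effectiveness half has variables in SAP 4.2.
- A reader might infer that the four best results could be picked from a larger number of treated women, and put a probability on a favourable 4/4 that way. Every recipient belongs to the FAS, so leaving any out would breach the SAP, and untreated women have no device outcome to select on. The open risk is selection before treatment. The documents give no basis for quantifying it and no evidence that it occurred.

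**Conclusion.** The point holds in this form: no variable is designated for the feasibility half of the SAP's primary objective, and the analysis set starts too late to supply a denominator for it. Followed exactly, the plan yields a receipt rate of 4/4 that carries no information. It can yield a rate of correct placement among recipients if SAP 4.3 is used that way. It cannot yield uptake or time to deployment. The gap in uptake could be nil or large: 100% down to 50% for zero to four eligible untreated women, a range that is assumed throughout.

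The documents also disagree on rank: feasibility is part of the primary objective in SAP 1.1 and secondary in Protocol section 2. The absence of a consecutive-enrolment rule means that selection before treatment cannot be excluded, which is a weaker statement than saying that it happened.

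**What to change.** In the SAP:

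- Define the FAS as all women in whom placement was attempted, and reword the safety population, which is now tied both to the FAS and to completed placement.
- Add per-woman fields: attempted (Y/N), fully inflated and correctly placed (Y/N), time from decision to full inflation, number of repositionings.
- Report successful/attempted and attempted/eligible as counts.

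In the protocol:

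- State that the four are the first four consecutive eligible women in whom the device was used or attempted. This keeps the fixed sample of 4.
- From December 2024 until the fourth patient is enrolled, and no later than April 2025, log every eligible woman not treated, with the reason. Oral consent is an inclusion criterion in Protocol section 4, so the log should say how a refusal is counted.

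In both documents, give feasibility the same rank in SAP 1.1 and Protocol section 2.

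SAP section 6 speaks of extraction from medical records in the past tense. If the cases have already been treated, look for eligible untreated women in those records where possible, and state as a limitation whatever cannot be recovered. Time from decision to inflation may be among the items lost.

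The cost is a few form fields, a short log, SAP wording and a small protocol change for the enrolment rule. The feasibility figure may then fall below 100%.

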1.2. Secondary Objectives

- To evaluate the safety profile of the AAJT-S device (device-related complications, thrombotic events, ischemic injuries, infection).
- To assess the duration of bleeding control and time to definitive surgical intervention.

2. Study Design

- **Design:** Prospective, single-center, open-label, non-randomized, proof-of-concept study.
- **Sample Size:** 4 patients
- **Analysis Type:** Descriptive statistics only. No inferential testing or hypothesis-driven comparisons will be performed due to small sample size and exploratory nature.

3. Analysis Populations

- **Full Analysis Set (FAS):** All patients who received AAJT-S for refractory PPH.
- **Safety Population:** Identical to FAS; all patients who underwent device placement and were monitored until discharge.

4. Variables

4.1. Baseline Characteristics

- Age (years)
- Gravida and Para
- Gestational Age at delivery (weeks + days)

4.2. Effectiveness Outcomes

- **Time to bleeding control** (minutes from inflation to cessation of visible bleeding)
- **Total duration of AAJT-S placement** (minutes)
- **Definitive surgical interventions performed** (Yes/No; type of procedure)
- **Total cumulative measured blood loss (CMBL)** (mL)
- **Need for blood transfusion** (Yes/No; units PRBC and FFP)

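### Total cumulative blood loss, the only blood volume outcome in SAP 4.2, mixes loss before and after the device, and the haemodynamic objective has no variable

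*SAP*

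**What the plan says.** Protocol section 4 admits women with "Primary PPH with blood loss >1000 mL" whose bleeding has not responded to drugs and balloon tamponade. Protocol section 6 gives the trigger for the device: "AAJT-S deployed in case of ongoing bleeding >1000 mL". The same section provides for surgery if bleeding resumes.

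Protocol section 7 names "Total blood loss and transfusion requirements" as a secondary outcome. SAP 4.2 carries this forward among the effectiveness outcomes as "Total cumulative measured blood loss (CMBL"), one figure in mL per woman. Neither document says when measurement starts or ends, and neither lists loss at inflation or at deflation. SAP 5.1 summarises continuous variables by median and range.

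The baseline variables in SAP 4.1 are age, gravida and para, and "Gestational Age at delivery (weeks + days"). Protocol section 2 sets a secondary objective, "To evaluate maternal hemodynamic stabilization and procedural outcomes". No outcome in protocol section 7, and no variable in SAP 4.1 to 4.3, names blood pressure, heart rate or an equivalent.

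**The concern.** An effectiveness outcome should describe what happens after the intervention. Here more than 1000 mL must be lost before the intervention can start, and that volume counts towards the outcome. Blood lost after deflation, including during any surgery, enters the same figure. Two women with the same total may have had very different courses once the device was inflated.

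The study has no comparison group, so each woman's course before and after inflation is the only contrast available. An unsplit total discards that contrast for the one outcome measured as a volume. A published median total could then be read as a result of the device when much of it arose beforehand.

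The haemodynamic gap is a separate matter. An objective with no listed variable may go unreported, or may be reported from measurements chosen after the results are known.

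**Working it through.** **Plan's own figure.** There is none to reproduce. The protocol states "Sample Size: 4 patients" and "no hypothesis testing or power calculation due to pilot nature", and no expected blood loss appears in either document. The check is therefore whether the listed variables identify loss after the device.

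**Inputs.**
- Pre-device loss P > 1000 mL (protocol sections 4 and 6).
- Total T: the only volume listed (SAP 4.2). The documents give no values, so those below are assumptions over a range.
- Loss from inflation onward, D: not listed. It is the sum of loss during inflation and loss after deflation.

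**Step 1: bounds for one woman.** T = P + D with P > 1000 and D ≥ 0, so 0 ≤ D < T − 1000. The share of the total that is certain to precede the device exceeds 1000/T.

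| Assumed T (mL) | Possible D (mL) | Certain pre-device share |
|---|---|---|
| 1250 | 0 to <250 | >80% |
| 1500 | 0 to <500 | >67% |
| 2000 | 0 to <1000 | >50% |
| 2500 | 0 to <1500 | >40% |
| 3000 | 0 to <2000 | >33% |

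As the total rises, the guaranteed pre-device share falls, but the range of possible loss after inflation widens.

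**Step 2: the planned summary for four women.** Take assumed totals of 2000, 2200, 2400 and 2600 mL. The median is (2200 + 2400)/2 = 2300 mL and the range is 2000 to 2600 mL. Two splits give exactly these totals:

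- Split A: P = 1100, 1200, 1300, 1400 and D = 900, 1000, 1100, 1200. Median D = (1000 + 1100)/2 = 1050 mL.
- Split B: P = 1900, 2100, 2300, 2500 and D = 100 in every woman. Median D = 100 mL.

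The planned median and range are identical under A and B. Listing the individual totals case by case, as protocol section 8 intends, does not separate them either. Only a value of P for each woman does, because then D = T − P.

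**Step 3: objective against variables.** Setting protocol section 2 beside protocol section 7 and SAP 4.1 to 4.3 shows no entry for haemodynamic status at any time. The data-capture line in protocol section 6 gives only general categories.

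**The case against.** Several points can fairly be made for the plan.

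- **Total loss is not the only bleeding outcome.** A reader might infer that the study has no usable bleeding outcome. It does: SAP 4.2 also lists time to bleeding control, counted from inflation. It contains no pre-device loss and corresponds to the protocol's primary outcome of control within 2 minutes. This stands. Its weakness is that the end point is when bleeding is no longer seen, judged in an open-label study. A volume split at inflation would support it.
- **Not listed does not mean not recorded.** A reader might infer that pre-device loss and vital signs were never captured. The documents show only that they are not analysis variables. Applying the 1000 mL criterion requires some assessment of loss before the device, and SAP section 6 draws the data from medical records. This stands, and makes the remedy easier.
- **The total need not mostly reflect late use of the device.** The arithmetic guarantees a majority pre-device share only for totals of 2000 mL or less, and the documents give no totals.
- **The starting point of the total is inferred.** No start is defined. That the total includes pre-device loss is the plain reading of the words, not an explicit statement.
- **The plan claims little.** It is descriptive, reports by case, and SAP section 7 acknowledges the small sample, the lack of controls and observer bias in blood loss. These limitations do not mention that the total includes pre-device loss, so they do not answer the point.

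**Conclusion.** The concern holds in a limited form. As defined, total cumulative loss does not measure bleeding after the device and should not stand as an effectiveness outcome on its own. For assumed totals of 1250 to 3000 mL, the upper limit on loss after inflation runs from just under 250 to just under 2000 mL, with zero always possible. This rests on the total starting before the device and on the entry and deployment criteria being followed.

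Independently of that, the haemodynamic objective has nothing specified to report.

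The primary outcome is untouched. It would go too far to conclude that splitting the volume would show a device effect: with four women, no control group and possible surgery after deflation, the split describes bleeding after the device and proves nothing about cause. The change is worth making, but the study does not fail without it.

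**What to change.** In SAP 4.2, define when measurement of cumulative loss starts and ends, and list three readings: at inflation, at deflation and at end of measurement. Report per woman the loss before inflation, during inflation and after deflation. Make loss from inflation onward the descriptive effectiveness outcome, and keep the total as a description of case severity.

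Add blood pressure and heart rate just before and after inflation, taken from the routine record, as the variables for the haemodynamic objective, and name a matching outcome in protocol section 7.

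Where a value was not charted, report it as missing, in line with the no-imputation rule in SAP 5.2, and do not present the total as evidence of effectiveness for that woman. Add to SAP section 7 that the total includes loss before the device.

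The cost is a little more data extraction, with no new procedure and no change in care. The SAP already singles out blood loss and time intervals for double-checking. The drawback is possible gaps: SAP section 6 describes extraction in the past tense, so data collection may be complete, and values at inflation and deflation can then be recovered only where they were charted.

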4.3. Safety Outcomes

- **Thrombotic events** (Yes/No)
- **Ischemic injury** (Yes/No)
- **Device-related complications** (e.g., skin necrosis, incorrect placement)
- **Infectious complications** (e.g., sepsis, wound infection)
- **Readmissions** or complications during postpartum follow-up (Yes/No)

5. Statistical Methods

5.1. Descriptive Analysis

- **Continuous variables:** summarized using **median, range (min–max)**.
- **Categorical variables:** presented as **counts and percentages**.

5.2. No inferential statistics

- Given the small sample size, **no hypothesis testing, p-values, or confidence intervals** will be calculated.
- No missing data imputation will be applied. All available data will be included in descriptive summaries.

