5.3. Software

- All analyses will be performed using **Microsoft Excel (Version 16.83)**. No specialized statistical software was used due to the simplicity and exploratory nature of the data.

6. Data Handling and Quality Assurance

- Clinical data were extracted from patient medical records and entered manually into a study-specific Excel spreadsheet.
- Double-checking was conducted for critical variables (e.g., blood loss, time intervals) by both study investigators.

7. Limitations

- Small sample size prevents generalizability.
- No control group.
- Estimates of blood loss may be subject to observer bias.

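### SAP 5.2 rules out confidence intervals because of small size, so 0/4 or 4/4 would be reported with no precision; exact intervals are a cheap, minor improvement

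*SAP*

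**What the plan says.** The study has one arm and 4 patients (Protocol 3, SAP 2). SAP 5.2, headed "No inferential statistics", cites the small sample and excludes "no hypothesis testing, p-values, or confidence intervals". SAP 2 states: "No inferential testing or hypothesis-driven comparisons will be performed due to small sample size and exploratory nature". Protocol 8 limits the analysis to descriptive statistics, excludes hypothesis testing and a power calculation because this is a pilot, and has outcomes shown case by case. Neither SAP 2 nor Protocol 8 mentions intervals, so the ban stands in SAP 5.2 alone.

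Under SAP 5.1, categorical variables are given as "counts and percentages". SAP 4.3 lists five safety items, three of them marked yes/no. SAP 7 says "Small sample size prevents generalizability". Neither document says what event rate would remain plausible if no events were seen.

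**The concern.** Small numbers rule out large-sample approximations. They do not rule out an exact interval; they make it wide, and the width is what the reader needs to see.

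This matters most for safety, which is part of the protocol's primary objective and is a secondary objective in SAP 1.2. If no patient has a given complication, the plan yields 0 (0%). If bleeding stops within 2 minutes in every patient, that outcome, reported in the protocol's binary form, yields 4 (100%). Either percentage can be read as firmer than it is. The caveat in SAP 7 is about carrying the result over to other patients. It does not say how imprecise the estimated rate is.

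**Working it through.** **Inputs.** n = 4 (Protocol 3, SAP 2). The documents give no confidence level, so 95% is assumed. They give no power calculation, precision target or results, so there is no figure of theirs to reproduce.

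**Exact (Clopper-Pearson) interval for x events in n patients.** The lower limit is the 0.025 quantile of Beta(x, n − x + 1), or 0 if x = 0. The upper limit is the 0.975 quantile of Beta(x + 1, n − x), or 1 if x = n. For n = 4:

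| x/n | two-sided 95% interval |
|---|---|
| 0/4 | 0 to 60.2% |
| 1/4 | 0.6 to 80.6% |
| 2/4 | 6.8 to 93.2% |
| 3/4 | 19.4 to 99.4% |
| 4/4 | 39.8 to 100% |

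The two extreme rows have closed forms. For 0/4 the upper limit is 1 − 0.025^(1/4) = 1 − 0.398 = 0.602. For 4/4 the lower limit is 0.025^(1/4) = 0.398. The 0/4 limit is also a one-sided 97.5% bound; the one-sided 95% bound is 1 − 0.05^(1/4) = 0.527.

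**Coverage at n = 4.** From the table, the interval for 0/4 misses the true rate only when that rate exceeds 60.2%, and the interval for 4/4 misses it only below 39.8%. Between these values no interval misses. Outside them only one tail can miss, with probability at most 2.5%. Minimum coverage is therefore 97.5%, and a numerical search over the true rate gave the same value. Shorter intervals cost coverage: the upper limit for 0/4 is 49.0% by Wilson and 44.5% by Jeffreys, but their minimum coverage at n = 4 is 83.0% and 86.6%.

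**Chance of no events in 4 on one outcome, (1 − p)^4, for an assumed true rate p.**
- p = 10%: 0.90^4 = 0.656
- p = 15%: 0.85^4 = 0.522
- p = 20%: 0.80^4 = 0.410
- p = 30%: 0.70^4 = 0.240

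The chance falls to one half at p = 1 − 0.5^(1/4) = 15.9%.

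**Smaller denominators (hypothetical).** With no events, 1 − 0.025^(1/n) gives 70.8% for n = 3 and 84.2% for n = 2.

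**Independence.** If patients are independent but differ in risk, the 0/4 limit still bounds the average risk, because the product of the (1 − p_i) is at most (1 − mean p)^4. With positive correlation (beta-binomial, assumed intraclass correlation 0.05, 0.10 or 0.20) it rises to 64.7%, 68.9% or 76.6%.

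**The case against.** The strongest reply is that this is a declared choice, applied consistently. The SAP does not call intervals invalid. The ordinary reading is that with 4 patients they add little and invite over-interpretation. Case-by-case presentation lets any reader see that 0% means none of 4, and no decision rule depends on an interval. The intervals at n = 4 span about 60 to 86 percentage points, so much of their message could be carried by one cautionary sentence in SAP 7.

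Most of this stands, and it keeps the point minor. It does not remove it. A case listing shows the denominator, but it leaves the reader to work out what the count excludes, and the plan requires no cautionary wording. An interval is not a test, so adding one leaves the descriptive design intact.

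Four stronger readings are tempting, and the documents do not support them.
- A reader might infer that the SAP rests on a mathematical mistake about small samples. It gives size as a reason and makes no claim about validity.
- A reader might infer that an absence of complications is likely even at a true rate of 20%. On one outcome it is the likelier result only up to about 15%; at 20% its chance is 41%. A clean record across all five items is no more likely than on any one of them.
- A reader might infer that late safety outcomes will have fewer than 4 patients. The Safety Population covers "all patients who underwent device placement and were monitored until discharge", Protocol 6 adds "phone monitoring post-discharge, pelvic ultrasound at 6 and 12 months postpartum", and SAP 5.2 says "All available data will be included in descriptive summaries". Losses are therefore possible, but none is documented. Stating n for each outcome is enough.
- A reader might infer that 60.2% is a firm ceiling after 0/4. It assumes independent patients, and positive correlation raises it.

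**Conclusion.** The point holds as a cheap, minor improvement to reporting. It does not correct an error: no figure or decision rule in the documents is wrong, and a descriptive analysis without tests is legitimate for 4 patients. What is missing is any measure of precision for binary outcomes in a study whose primary objective includes safety. Its size is the distance between a bare 0% and an upper limit of 60.2%, or between a bare 100% and a lower limit of 39.8%. These limits assume a two-sided 95% level and independent patients with a common risk. The 4/4 case applies to bleeding control only in the protocol's binary form, because SAP 4.2 records it as a time in minutes.

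**What to change.** **SAP 5.2.** Keep the exclusion of tests and p-values, adjust the heading to match, and replace the exclusion of intervals with:

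> *For the Protocol 7 primary outcome (bleeding controlled within 2 minutes) and for all five safety outcomes in SAP 4.3, each recorded as any event yes/no, report x/n, where n is the number of patients observed for that outcome, with the exact (Clopper-Pearson) two-sided 95% interval, assuming independent patients with a common risk. Outcomes with the same x/n share one footnote.*

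Naming all five items matters because device-related and infectious complications carry no yes/no mark in SAP 4.3 and could otherwise be left out.

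**SAP 2 and Protocol 8.** Use the same scope: descriptive statistics without hypothesis tests, with exact intervals for these six outcomes.

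**Start point.** Protocol 7 counts the 2 minutes from application of the device, while SAP 4.2 counts time to control from inflation. The two must be reconciled before the binary outcome is derived.

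**SAP 7.** Add:

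> *With 4 patients, event rates are estimated very imprecisely; absence of an observed complication does not establish a low rate.*

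**Cost.** No new data are needed. The limits can be computed in the planned Excel file: 1 − 0.025^(1/n) for zero events, beta quantiles otherwise. The Protocol 8 change is a small wording amendment to an ethics-approved protocol. The downside is that the intervals are very wide, repeat across outcomes and look less favourable.
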